7.1.2 Longitudinal Repeated Measures Analysis

A longitudinal repeated measures analysis using ‘direct likelihood’ will be performed. The SAS procedure PROC MIXED will be used. The preferred model will include the fixed categorical effects of treatment, week and treatment-by-week interaction as well as the continuous fixed covariates of baseline measurement and baseline measurement-by-week interaction.

The following model will be used:

$$C_{ijk} = \text{intercept} + \beta_1 [M_{\text{baseline},ij}] + \tau_i + \omega_m + \alpha_k + (\alpha \tau)_{ik} + (\alpha M_{\text{baseline}})_{ijk} + \text{error}_{ijk}$$

(Model 7.1.2.1)

where

- C_{ijk} is the change from baseline for subject j in treatment group i at time k,
- β_1 is the slope coefficient for the baseline measurement,
- $M_{\text{baseline},ij}$ is the baseline measurement of subject j in treatment group i,
- τ_i is the mean effect of treatment group i,
- ω_m is the mean effect of stratum m
- α_k is the mean effect at time k
- $(\alpha \tau)_{ik}$ is the interaction term between treatment group i and time k.
- $(\alpha M_{\text{baseline}})_{ijk}$ is baseline measurement-by-week interaction term for subject j in treatment group i at time k, and
- error_{ijk} is the error term for subject j in treatment group i at time k.

An unstructured matrix for the within-subject error variance-covariance will be used. The denominator degrees of freedom will be calculated according to the Kenward-Roger method.

In case of non-convergence of the preferred model or memory space issues, the following back-up models are defined:

- The first backup model is the same as the preferred model but the Kenward-Roger method will be replaced by Satterthwaite approximation.
- The second backup model is the same as the preferred model but without the term for baseline measurement-by-week interaction.

The second back-up model will only be provided if the first back-up model does not converge or has memory issues.

The model will provide least-squares mean estimates, standard errors and 2-sided 95% confidence intervals for mean change at all time points within and between treatments. Pre-specified stratification factors other than site in the randomization (e.g. pre-enrollment factor) will be added as an additional fixed effect in the mixed model.

Assessment of Treatment-by-Baseline Interaction:

Treatment-by-baseline interaction will be assessed for the analyses of the primary efficacy endpoint. In the repeated measures model (7.1.2.1), the interaction will be tested by including the additional terms for the treatment-by-baseline interaction.

The test for interaction will be performed at the 0.10 level of significance. If the treatment-by-baseline interaction is not significant, the original model (7.1.2.1) will be used. Otherwise, the interaction will be assessed as qualitative or quantitative. Assessment of the interaction type will be based on regression lines plotted for each treatment group. The intercepts and slopes for these regression plots will be obtained from the analysis model including the interaction term. The intercepts will be estimated by the least squares treatment means. The abscissa of the plots will range from the minimum baseline value from all subjects included in the analysis to the maximum baseline value.

If the regression lines do not cross, or the crossing is judged not severe (i.e., the crossing occurs near the boundary or beyond the range of baseline values), then the interaction will be considered quantitative and this does not compromise the validity of the treatment comparisons. In this case, the treatment comparisons will be made using the model without the interaction term.

Otherwise, the interaction will be considered qualitative and treatment comparisons will not be presented as a result of the complete model. In this case, the impact of the baseline value on treatment effect will be investigated by summarizing the data in subsets defined by baseline categories.

Subgroup Analyses and Assessment of Treatment-by-Subgroup Interaction:

Treatment effects will be assessed for subgroups based on age group, gender, race, region, and baseline HbA1c, as defined in Table 7.3.2A and Table 7.3.2B. The analyses will be based on model 7.1.2.1 with additional covariates of subgroups, treatment-by-subgroup, time-by-subgroup, and treatment-by-time-by-subgroup. Additionally, the treatment-by-stratification will be assessed. Tests of the treatment by subgroup interaction will be assessed using contrasts of the treatment effect by subgroups at Week 24. The model to assess the treatment-by-baseline HbA1c interaction will include baseline HbA1c as a continuous variable. Adjusted mean change from baseline and its difference from the control group will be given for each subgroup at week 24.

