5 SAMPLE SIZE AND POWER

The change from baseline in HbA1c at Week 24 will be assessed comparing co-administered saxagliptin 5 mg and dapagliflozin 10 mg plus metformin with or without SU versus titrated insulin glargine plus metformin with or without SU.

Power calculations for longitudinal repeated measures analyses depend on many factors, including the pattern of drop-outs over time and correlations among the various time points included in the model. The choice of these parameters will affect any estimates of power, and their true values may not be known. Based on comparisons of results of longitudinal repeated measures analyses and analysis of covariance (ANCOVA) using last observation carried forward (LOCF) from previous diabetes trials, the estimated standard errors of the treatment differences were similar between analyses. Therefore, power calculations are based on ANCOVA with LOCF, with the expectation that this will provide a good estimate of the power for the primary analysis using a longitudinal repeated measures model. To demonstrate non-inferiority of saxagliptin plus dapagliflozin to insulin for changes from baseline to Week 24 in HbA1c within a non-inferiority margin of 0.30%, assuming a standard deviation 1.1%, and at a one-sided significance level of 0.025, 284 evaluable subjects will be needed in each treatment group to provide approximately 90% power (given a true difference of zero between the 2 treatment

groups). Assuming that 5% of subjects do not have a post-baseline assessment, a total of approximately 598 subjects (299 subjects per treatment arm) need to be randomized. Assuming that 50% of screened subjects will fail to meet screening criteria, a total of 1196 subjects need to be screened.

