7.5 Efficacy

7.5.1 Overall Efficacy Summary

Efficacy analyses will be performed using the randomized subjects data set. For the non-inferiority endpoints, the analysis will also be performed in the evaluable subject data set. All analyses included in the hierarchical testing below, including the primary analysis, will use the randomized

subject data set. The analyses using the evaluable subject data set will not be included in the hierarchical testing.

All the main analyses will be conducted using values prior to rescue/intensification of treatment or treatment discontinuation. Values collected after this time will be excluded from analyses. Sensitivity analysis using data regardless of rescue or treatment discontinuation will also be performed for the primary efficacy endpoint to assess the robustness of the primary efficacy results.

The primary endpoint is the change in HbA1 from baseline at Week 24 visit. The primary endpoint will be tested for non-inferiority for saxagliptin plus dapagliflozin versus insulin at the $\alpha = 0.025$ level (one sided), within a non-inferiority margin of 0.30%. If non-inferiority is demonstrated for the primary endpoint, the statistical tests for the secondary efficacy endpoints will be performed. The secondary endpoints then will be tested sequentially in the order that they appear below and in the objectives section of the protocol. Each comparison will be tested at the $\alpha = 0.05$ (two-sided) level. Statistical tests between the dapagliflozin plus saxagliptin group and insulin group will be only performed for a given secondary endpoint if all previous sequential tests are statistically significant. Otherwise, the testing procedure will stop at the secondary endpoint that does not reach statistical significance. These secondary endpoints are all testing superiority, with the exception of the fourth and fifth bullets below which are testing non-inferiority.

- Change from baseline in total body weight at Week 24 (tested for superiority)
- Proportion of subjects with confirmed hypoglycemia [defined as: blood glucose ≤ 70 mg/dL (3.9 mmol/L) recorded in the hypoglycemia module of the CRF] at Week 24 (testing superiority)
- Proportion of subjects achieving a therapeutic glycemic response, defined as HbA1c $< 7.0\%$, without any reported hypoglycemia (for the duration of the Short-term Period) at Week 24 (testing superiority)

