7.5.2 Primary Efficacy Analysis

The primary endpoint is the change in HbA1 from baseline at Week 24 visit. The primary endpoint will be tested for non-inferiority for saxagliptin plus dapagliflozin versus insulin at the $\alpha = 0.025$ level (one sided). The primary analysis of the change in HbA1c from baseline at Week 24 visit will be based on a longitudinal repeated measures analysis using 'direct likelihood'. The model will use subjects in the primary efficacy data set (i.e., randomized subjects data set) who have a baseline assessment and at least one post-baseline open-label

treatment period assessment. The SAS procedure PROC MIXED will be used. The preferred model will include the fixed categorical effects of treatment, week, randomization stratification factor (background medication of metformin alone vs. metformin + SU) and treatment-by-week interaction as well as the continuous fixed covariates of baseline measurement and baseline measurement-by-week interaction (see Model 7.1.2.1 in Section 7.1.2). An unstructured matrix for the within-subject error variance-covariance will be used. The denominator degrees of freedom will be calculated according to the Kenward-Roger method. A number of back-up models are defined in the Core statistical analysis plan (Section 7.1.2) in case of non-convergence of the preferred model or other issues. Data collected outside the analysis window (defined in Section 8 of this SAP) after subjects discontinued study medication will also be excluded from the primary analysis. Point estimates and 95% confidence intervals for the mean change within each treatment group as well as the difference in mean change between the saxagliptin plus dapagliflozin versus insulin will be calculated. If the upper limit of the 95% confidence interval of the difference is $< 0.3\%$, then saxagliptin plus dapagliflozin as add-on therapy to metformin with or without SU will be considered non-inferior to insulin as add-on therapy to metformin with or without SU.

Sensitivity Analyses

The following sensitivity analyses will be carried out for the primary end point:

- Primary analysis will be repeated using Evaluable Subjects data set.
- Primary analysis will be repeated using all available values regardless of rescue or treatment discontinuation
- An ANCOVA analysis using values prior to rescue or treatment discontinuation (LOCF will be used if the week 24 value is not available)

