7.5.6 Summary of Primary Efficacy Endpoint within Subgroups

Treatment effects will be assessed for subgroups based on age group, gender, race, region, and baseline HbA1c, as defined in Table 7.3.2A and Table 7.3.2B. The analyses will be based on model 7.1.2.1 with additional covariates of subgroups, treatment-by-subgroup, visit-by-subgroup, and treatment-by-visit-by-subgroup. Additionally the treatment-by-stratification interaction will be assessed. The nominal p-value for subgroup-by-treatment interaction will be presented. The p-value for the test of treatment by age, female age, baseline HbA1c, and baseline eGFR interaction will include corresponding continuous subgroup variables in the model.

Adjusted mean change from baseline and its difference from the control group will be given for each subgroup at week 24.

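### A 0.10-level interaction pre-test in SAP Section 7.1.2 can withhold the primary comparison that Section 7.5.2 uses unconditionally; if followed, 90% power becomes about 81-82%

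*SAP*

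**What the plan says.** SAP Section 7.1.2, under its treatment-by-baseline heading, adds interaction terms to Model 7.1.2.1 for the primary endpoint. "The test for interaction will be performed at the 0.10 level of significance". Three branches follow:

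- Not significant: Model 7.1.2.1 is used as it stands.
- Significant, but the plotted lines do not cross, or "the crossing occurs near the boundary or beyond the range of baseline values": the interaction is called quantitative. "In this case, the treatment comparisons will be made using the model without the interaction term".
- Any other significant result: "Otherwise, the interaction will be considered qualitative and treatment comparisons will not be presented as a result of the complete model". Data are then summarised in baseline categories instead.

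Section 7.5.2 analyses the same endpoint with the same model and has one criterion: "If the upper limit of the 95% confidence interval of the difference is" below 0.3%, the combination is non-inferior. It does not mention the interaction step. Section 7.5.1 makes the secondary hierarchy depend on that result: "If non-inferiority is demonstrated for the primary endpoint, the statistical tests for the secondary efficacy endpoints will be performed". Section 5 sizes the trial with no allowance for a pre-test: "284 evaluable subjects will be needed in each treatment group to provide approximately 90% power", at a true difference of zero.

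**The concern.** The two sections give different rules for one decision. Under Section 7.5.2 a trial whose upper limit is below 0.3% has succeeded. Under Section 7.1.2 the same trial may have no primary comparison to present. Nothing ranks one section above the other, and nothing says what happens to the secondary hierarchy when the comparison is withheld.

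The gate is also loosely fixed. The term *complete model* is not defined, and closeness to the edge of the baseline range is judged from a plot. Moreover, a crossing marks the baseline value at which the estimated difference is zero, whereas the primary hypothesis asks whether the difference reaches +0.30. When the arms are truly equal, which is the case the trial is sized for, almost any chance slope difference makes the lines cross near the middle of the data. The gate therefore bites hardest under the planning assumption.

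**Working it through.** **Inputs from the SAP.** Margin 0.30, SD 1.1, 284 evaluable per arm, one-sided 0.025, true difference 0 (Section 5); pre-test level 0.10 (Section 7.1.2); screening HbA1c 8% to 12% (Section 2.1). The spread of baseline HbA1c is not given and is assumed below.

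**1. The plan's own figure.** SE = 1.1 × √(2/284) = 0.0923. Power = Φ(0.30/0.0923 − 1.96) = Φ(1.29) = 90.1%. The stated 90% reproduces.

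**2. Simple approximation with the gate.** With no true interaction the pre-test is significant in 10% of trials. If each of these is withheld, power is 0.901 × 0.90 = 81.1%.

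**3. Why nearly all of them are withheld.** The fitted lines cross |Zd/Zb| baseline SDs from the baseline mean, where Zd and Zb are the standardised estimates of the treatment difference and the slope difference. A significant test means |Zb| > 1.645. At a true difference of zero, a crossing more than one SD from the mean needs |Zd| > |Zb| > 1.645. Both exceed 1.645 in 0.10 × 0.10 = 1% of trials, and in half of those |Zd| is the larger: 0.5%, or 5% of the significant results. The other 95% cross within one SD of the mean.

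**4. Simulation.** Week 24 ANCOVA (the approximation Section 5 itself uses), no true interaction, 20,000 trials per scenario, Monte Carlo SE about 0.3 points. The comparison is withheld if the interaction p-value is below 0.10 and the crossing lies inside the observed baseline range after an edge allowance is removed at each end. A withheld trial counts as non-inferiority not shown. Power (%):

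| Rule | Uniform, mean 10.0, SD 1.15 | Mean 9.5, SD 0.80 | Right-skewed, mean 8.8, SD 0.59 |
|---|---|---|---|
| No gate (Section 7.5.2 alone) | 90.5 | 90.1 | 89.7 |
| Gate, 0% edge allowance | 81.5 | 81.0 | 81.1 |
| Gate, 10% | 81.5 | 81.0 | 81.4 |
| Gate, 20% | 81.7 | 81.2 | 84.4 |
| Gate, 25% | 81.9 | 81.7 | 86.6 |

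The share of trials withheld is 9.0-9.9% at a 0-10% allowance, 5.9-9.5% at 20% and 3.6-9.1% at 25%.

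A separate simulation (12,000 trials for each of four assumed baseline shapes) gave 80.6-81.5% when any crossing in the range counts. With 30% removed at each end it gave 81.5-83.3% for the three less skewed shapes and 87.2% for a strongly skewed one.

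**5. Other true states.**

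- Difference +0.30 (type I error): 2.2-2.3% with the gate, 2.4-2.6% without.
- Difference −0.10: power 89-95% with the gate, 99% without.
- Difference −0.30: 92-99% with the gate, 100% without.
- True slope difference of 0.05 per 1% HbA1c: 4-17% of trials withheld, power 75-86%. For the skewed baseline the largest true difference anywhere in 8-12% is 0.05 × (12 − 8.8) = 0.16, still below the margin.

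**The case against.** The strongest reply is that *complete model* means the model with the interaction term, so that only its output is barred; Section 7.5.2 is then untouched and no power is lost. The wording allows this. But the preceding branch grants use of the model without interaction specifically when the interaction is quantitative, the withheld branch is set against that permission, and its only replacement is summaries by baseline category. The narrow reading fits poorly, and a primary decision rule should not depend on it.

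Second, Section 7.1.2 speaks of presentation and never says that a withheld comparison means non-inferiority was not shown. That is true. The power figures rest on that further condition, and the SAP's silence on it is part of the defect.

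Third, Section 7.1.2 may be generic text (the amendment history records insertion of core SAP text), and a trial-specific section would ordinarily prevail. Section 7.1.2 names the primary endpoint, however, and no precedence is stated.

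Fourth, Section 7.1.2 does not say that the plotted lines are those at Week 24. If they pool visits and the arms differ early, crossings move away from the centre. A five-visit simulation with an assumed residual correlation of 0.7 and a zero Week 24 difference gave gated power of about 81-86% for an assumed visit-averaged difference of −0.15, and about 83-90% for −0.30. The loss could therefore be smaller than the Week 24 calculation shows.

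Finally, overall estimates would survive in the sensitivity analyses (ANCOVA with LOCF, return-to-baseline imputation, tipping point), and Section 7.5.6 provides "Adjusted mean change from baseline and its difference from the control group will be given for each subgroup at week 24". None of these is the test that decides the primary hypothesis.

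**Conclusion.** The point holds: the plan is wrong as written and should be fixed. Sections 7.1.2 and 7.5.2 give incompatible rules for the primary comparison, and neither is given precedence. That follows from the text and needs no assumption.

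The size is conditional. It requires that Section 7.1.2 is followed, that a withheld comparison counts as non-inferiority not shown, that the true difference is zero, and that the lines are read at Week 24. Power is then about 81-82% on ordinary readings and up to about 87% on lenient ones with a skewed baseline, against the stated 90%. The assumed baseline spread matters mainly for the lenient readings. False claims do not become more likely, and the loss shrinks if the combination is truly better.

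**What to change.** In Sections 7.1.2 and 7.5.2, state that the Model 7.1.2.1 comparison against 0.30% is always presented and alone decides the primary hypothesis and entry to the secondary hierarchy. Delete the sentence that withholds treatment comparisons. Keep the treatment-by-baseline test and the planned baseline-HbA1c subgroup estimates as supportive. Optionally, read them against +0.30 rather than against a crossing at zero.

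The cost is SAP wording only, since the supportive output is already planned. There is one small downside: if a real interaction exists, the average effect is still the headline result, with the subgroup results shown beside it.

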7.1.3 Analysis of Covariance (ANCOVA)

In summaries of efficacy endpoints examining *changes from baseline at Week 24*, ANCOVA of the differences between post-baseline and baseline measurements will be performed, with treatment group as an effect and the baseline measurement as a covariate.

The following ANCOVA model will be used:

$$D_{t,ij} = \text{intercept} + \beta [Y_{0,ij}] + \tau_i + \omega_m + \text{error}_{ij} \quad \text{Where (Model 7.1.3.1)}$$

- $D_{t,ij} = Y_{24,ij} - Y_{0,ij}$ = the Week 24 change from baseline of subject j in treatment group i (as defined in Section 7.1.1.2 and Section 8 on conventions),
- $Y_{0,ij}$ is the baseline measurement of subject j in treatment group i ,
- $Y_{24,ij}$ is the Week 24 measurement of subject j in treatment group i ,
- β is the slope of $D_{t,ij}$ regressing on the baseline measurement and,
- τ_i is the mean effect of treatment group i .
- ω_m is the mean effect of stratum m , and
- *Intercept*, β and τ_i are unknown parameters to be estimated from the data.

The model will provide least squares mean estimates and 2-sided 95% confidence intervals for mean changes from baseline within and (when warranted) differences in mean change from baseline between treatments. Where applicable, t-statistics corresponding to the Type III sums of squares for the differences in the least squares means will be used to obtain p-values for treatment group comparisons.

7.1.4 Descriptive Summaries of Continuous Variables

Descriptive summaries of continuous variables in terms of change or percent change from baseline values will be provided, including ns, means, medians, and standard error (SE). In addition, 95% confidence interval for the mean (percent) change from baseline will be calculated for continuous efficacy variables. They will be presented by treatment group and time point where applicable.

7.1.5 Descriptive Summaries of Categorical Variables

Descriptive summaries of categorical variables will consist of frequencies and percentages for each treatment group and overall, where applicable.

7.1.6 Descriptive Summaries of Change from Baseline in Categorical Variables

Descriptive summaries of change from baseline in categorical variables will be provided using shift tables. Frequencies and percentages of subjects within each treatment group will be generated for levels of cross-classifications of baseline and the on-treatment value of the parameter. The on-treatment value can either be the value at a certain time point, or e.g. for laboratory tests, the minimum/maximum value in the direction of toxicity, which has been observed during the short-term treatment period. Treatment group differences will not be assessed in summaries of shifts.

7.1.7 Kaplan-Meier Curve and Estimates for Time-to-Event Analyses

Kaplan-Meier plots² of time to event variables will be displayed by treatment group. Unless otherwise specified, the plot will be presented only when there are at least 5 events in one treatment group. Additionally, a table will accompany the plot and will display the Kaplan-

Meier estimates of the cumulative proportion (with 95% CI calculated based on Greenwood's method³ when applicable) of subjects with event at specific time points by treatment group. If the estimated lower bound of 95% CI is below 0 or the estimated upper bound of 95% CI is over 1, then it will be restricted to 0 or 1 respectively.

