2.2 Treatment Assignment

CCI

Subjects entering the 24-week open-label short-term treatment period

Following completion of the lead-in period, subjects who meet the criteria will be randomly assigned by the IVRS at the Day 1 Randomization visit, to one of the following two (2) open-label treatment arms in a 1:1 ratio:

- saxagliptin 5 mg and dapagliflozin 10 mg
- titrated insulin glargine

Randomization will be stratified by current use of background medication (metformin alone vs. metformin plus SU) at baseline to ensure equal representation across all treatment groups and also within the sub-study. Subjects will continue to receive their stable dose of metformin with or without SU throughout the study.

During the first 12 weeks following randomization, there will be no protocol specified rescue criteria. During this time, subjects receiving open-label insulin glargine will be titrated to target, which is driven over an (8) week period, then at Investigator's discretion with minimal adjustment recommended. Titration of open-label saxagliptin and dapagliflozin will not be allowed at any time during the study.

Subjects entering the 28-week open-label long-term treatment period

Subjects who complete the Short-term Treatment Period will continue into the Long-term Period taking the same open-label study medication (saxagliptin 5 mg QD and dapagliflozin 10 mg QD or insulin glargine) that they were randomized to on study Day 1. Subjects will continue to receive their stable dose of metformin with or without SU throughout the study.

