4.3 Exploratory Endpoints

- 1) In a sub-study, change from baseline in mean amplitude of glucose excursions (MAGE) of 24 hour glucose readings measured by Continuous Glucose Monitoring (CGM) at Week 2, Week 12, and Week 24 (Phase V[®] CGM Analytics variable name MAGE_SC see appendix 1).
- 2) In a sub-study, change from baseline in the mean value of 24 hour glucose readings measured by Continuous Glucose Monitoring (CGM) at Week 12 and Week 24 (Phase V[®] CGM Analytics variable name BGMEANALL see appendix 1).
- 3) In a sub-study, change from baseline within-subject, within-day in the standard deviation of 24 hour glucose readings measured by Continuous Glucose Monitoring (CGM) at Week 2, Week 12 and Week 24 (Phase V[®] CGM Analytics variable name WPWDSDDY see appendix 1).
- 4) In a sub-study, change from baseline in the percentage of time spent in the euglycemic target range of \geq 71 mg/dL (3.9 mmol/L) and \leq 180 mg/dL (10.0 mmol/L) as measured by CGM at Week 2, Week 12, and Week 24 (Phase V[®] CGM Analytics variable name CGM_GE71_LE180_PCTTIME see appendix 1).
- 5) In a sub-study, change from baseline in the percentage of time spent with glucose \leq 70 mg/dL (3.9 mmol/L) as measured by CGM at Week 2, Week 12, and Week 24 (Phase V[®] CGM Analytics variable name CGM_HYPO_PCTTIME see appendix 1).
- 6) In a sub-study, change from baseline in the percentage of time spent with glucose \leq 70 mg/dL (3.9 mmol/L) as measured by CGM between midnight (12am) and 6am at Week 2, Week 12, and Week 24 (Phase V[®] CGM Analytics variable name CGM_NOC_HYPO_PCTTIME see appendix 1).
- 7) Change from baseline in HbA1c at Week 52.
- 8) Change from baseline in total body weight at Week 52
- 9) Proportion of subjects with confirmed hypoglycemia [defined as: blood glucose \leq 70 mg/dL (3.9 mmol/L) recorded in the hypoglycemia module of the CRF] at Week 52

- 10) Proportion of subjects achieving a therapeutic glycemic response, defined as HbA1c < 7.0%, without any hypoglycemia, at Week 52
- 11) Proportion of subjects achieving a therapeutic glycemic response, defined as HbA1c < 7.0%, at Week 52
- 12) Proportion of subjects requiring rescue or discontinuation for lack of glycemic control) at Week 24 and Week 52
- 13) Time to treatment intensification (addition of non study insulin or other anti-diabetic therapies for rescue therapy or discontinuation for lack of glycemic control) at Week 24 and Week 52

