7.5.5.2 Glycemic Rescue or Discontinuation from Study treatment due to Lack of Efficacy

The proportion of subjects requiring treatment intensification (glycemic rescue or discontinue study treatment for lack of efficacy) up to Week 24 / 52 will be assessed by summarizing the difference in the percentages between treatment groups and by a time-to-event analysis using the Kaplan-Meier methodology.

Time to treatment intensification will be analyzed using a Cox proportional hazards model. Estimates of hazard ratio and 95% confidence intervals will be provided. Kaplan-Meier plots^{□1} of time to intensification at Weeks 24 and 52 will be calculated and plotted by treatment group. Unless otherwise specified, the plot will be presented only when there are at least 10 events in one treatment group. Additionally, a table will accompany the plot and will display the Kaplan-Meier estimates of the cumulative proportion (with 95% CI calculated based on Greenwood's method^{□2} when applicable) of subjects with event at specific time points by treatment group. If the estimated lower bound of 95% CI is below 0 or the estimated upper bound of 95% CI is over 1, then it will be restricted to 0 or 1 respectively. For the analysis during 24 / 52 weeks, all subjects will be censored at Week 24 / 52 visit (end of ST treatment/end of LT treatment) if treatment intensification has not occurred by then. Subjects rescued at Week 24 / 52 will be counted as having an event for the analysis.

Composite response endpoints (glycemic control without hypoglycemia), will be analyzed using logistic regression with adjustment for baseline HbA1c value and/or the stratification factor. None of the exploratory endpoints will be statistically tested

In addition, an analysis of the proportion of subjects not rescued and achieving glycemic response (defined as HbA1c < 7%) in subjects from the Short-term Completers Data Set at time points during the LT period will be performed using the same methodology described above (with adjustment for end of ST HbA1c measurement). Subjects discontinued or missed measurements (regardless of the type of missing) at the specific time point will be considered as not achieving glycemic response.

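### The Kaplan-Meier confidence limits are implicitly plain-scale Greenwood limits, which sit too low when an arm has few events by the reported time point

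*SAP*

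**What the plan says.** Section 7.1.7 sets the general method for time-to-event tables: Kaplan-Meier cumulative proportions at specific time points, with "95% CI calculated based on Greenwood's method" and the qualifier *when applicable*. No transformation is named. A boundary rule covers the case "If the estimated lower bound of 95% CI is below 0 or the estimated upper bound of 95% CI is over 1". Any such limit is replaced by the bound that it crosses. Section 7.5.5.2 repeats the rule for treatment intensification: "of subjects with event at specific time points by treatment group. If the estimated lower bound of 95% CI is below 0".

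The display thresholds differ. The general rule, unless otherwise specified, is that "the plot will be presented only when there are at least 5 events in one treatment group". For treatment intensification, "the plot will be presented only when there are at least 10 events in one treatment group". Each threshold needs to be met in one arm only.

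The endpoint using this table is exploratory endpoint 13 in section 4.3, at Weeks 24 and 52: "Time to treatment intensification (addition of non study insulin or other anti-diabetic therapies for rescue therapy or discontinuation for lack of glycemic control". Section 7.5.5 says exploratory endpoints are not tested. Section 7.5.5.2 also gives a Cox hazard ratio with its confidence interval.

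**The concern.** A symmetric interval around a small proportion fits the sampling distribution poorly. The standard error shrinks with the estimate, so a sample with too few events gives an interval that is both too low and too narrow. With no events, Greenwood's variance is zero and the interval collapses to a point.

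The display rule does not prevent sparse cells. One arm can meet the threshold while the other has very few events, and an early row can be sparse in both arms. Section 2.2 adds that for the first 12 weeks "there will be no protocol specified rescue criteria", which makes few early events plausible but does not establish it.

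At stake is whether limits printed as 95% deserve that label. The error mostly runs one way: the upper limit is too low in the arm with fewer events. Section 7.1.8 already switches to exact intervals for binary endpoints with fewer than 5 responders in an arm; the Kaplan-Meier sections have no such provision.

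**Working it through.** **Inputs.** Section 5 gives 284 evaluable and 299 randomized subjects per arm; the step between them reproduces: 284 / 0.95 = 298.9, so 299. The SAP gives no intensification rate and no coverage figure. The true rates below are assumptions.

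**Which scale.** Log-log limits always lie between 0 and 1. A rule for limits outside that range therefore has a use only on the plain scale.

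**Formulas, no censoring before the time point.** With x events in n subjects, p = x/n and S = 1 − p:
- Plain: Greenwood's variance reduces to p(1 − p)/n, so the limits are p ± 1.96 √(p(1 − p)/n), cut at 0 and 1.
- Log-log: 1 − S^exp(∓t), with t = 1.96 √((1 − S)/(nS)) / |ln S|.
- Exact upper limit at zero events: 1 − 0.025^(1/n).

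**One event in 299.** p = 0.334% and SE = 0.334%. The plain limits are 0.334 ± 0.654, that is −0.32% to 0.99%, printed as 0 to 0.99%. For log-log, ln S = −0.00335 and t = 1.96. The limits are 1 − exp(−0.00335 × 0.141) = 0.05% and 1 − exp(−0.00335 × 7.10) = 2.35%.

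**Other counts, n = 299.**

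| Events | Plain, cut at 0 | Log-log |
|---|---|---|
| 0 | 0 to 0% | undefined; exact 0 to 1.23% |
| 1 | 0 to 0.99% | 0.05 to 2.35% |
| 3 | 0 to 2.13% | 0.32 to 3.08% |
| 5 | 0.22 to 3.13% | 0.70 to 3.97% |
| 10 | 1.31 to 5.38% | 1.81 to 6.13% |
| 30 | 6.63 to 13.44% | 7.12 to 14.04% |

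The cut at 0 acts only at 1 to 3 events.

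**Exact coverage.** This is the sum of binomial probabilities over every x whose interval contains the true rate.

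| Assumed true rate | Expected events, n = 299 | Plain, n = 299 | Plain, n = 284 | Log-log with exact limit at zero, n = 299 |
|---|---|---|---|---|
| 0.3% | 0.9 | 59% | 57% | 94% |
| 0.5% | 1.5 | 78% | 76% | 94% |
| 1% | 3.0 | 80% | 94% | 97% |
| 1.25% | 3.7 | 88% | 87% | 94% |
| 1.5% | 4.5 | 93% | 92% | 95% |
| 2% | 6.0 | 93% | 92% | 96% |
| 3% | 9.0 | 94% | 92% | 96% |
| 5% | 15.0 | 92% | 94% | 96% |

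At 0.3% and 0.5% nearly all misses are samples with no events. The chance of none in 299 is 0.997^299 = 41% and 0.995^299 = 22%.

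The 1% row depends on n through discreteness. The upper limit for 1 event is 0.99% at n = 299, just missing 1%, and 1.04% at n = 284, just covering it.

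**With censoring.** A simulation with n = 299, an assumed 10% censoring and 20,000 runs gave plain coverage of 76% at 0.5%, 92% at 1%, 92% at 2% and 94% at 5%. Log-log with the exact limit at zero gave 94%, 97%, 97% and 96%.

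**The case against.** Plain Greenwood limits are a standard choice, and the boundary rule is clear to a programmer. The table is descriptive: no exploratory endpoint is tested, and the between-arm comparison rests on the Cox hazard ratio and the difference in percentages. That stands and keeps the point minor.

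Three stronger readings are tempting, and the document does not support them.

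- *That very low rates are expected.* The SAP states no rate. The absence of protocol rescue criteria before Week 12 does not rule out rescue, and discontinuation for lack of glycemic control also counts as an event. The named time points are Weeks 24 and 52; no earlier row is fixed. The intensification threshold is 10 events in one arm (10/299 = 3.3%), so a near-empty other arm is possible but not predicted.
- *That truncation causes the shortfall.* It removes only impossible values and cannot lower coverage. The symmetric scale is the fault.
- *That the separation between arms is generally overstated by much.* Both arms' limits move down together. For 3 against 10 events, the distance from the first arm's upper limit to the second's lower limit is 1.31 − 2.13 = −0.82 points on the plain scale and 1.81 − 3.08 = −1.27 on the log-log scale, a change of about 0.4 points. At 1 against 10 events the change is larger: 1.31 − 0.99 = 0.32 against 1.81 − 2.35 = −0.54, about 0.9 points.

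The qualifier *when applicable* may be meant to leave out zero-event points. If so, the zero-width interval never appears, but the text does not say this.

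**Conclusion.** The point holds in limited form. The truncation rule implies plain-scale limits, and these sit too low when an arm has few events by the reported time point. The shortfall is serious at assumed true cumulative rates of roughly 1.25% and below, about 4 or fewer expected events in 299. Even there, the 1% figure swings between 80% and 94% with n and should not be quoted alone. At rates of 1.5% to 5% the shortfall is mild.

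The coverage table assumes no censoring before the time point; the censored simulation shows the same broad pattern. The zero-width result assumes that zero-event points are displayed. The consequence is mislabelled descriptive intervals where events are sparse. The primary analysis, the hierarchical tests and the Cox hazard ratio are unaffected.

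**What to change.** In sections 7.1.7 and 7.5.5.2, state that pointwise 95% intervals use the complementary log-log transformation with Greenwood's variance, and that the exact binomial upper limit is shown when an arm has no events by the time point. The second statement is needed because log-log limits are undefined at zero events; it also settles what *when applicable* leaves open. Delete the truncation sentence in both places, since it is then not needed. The cost is two sentences and one software option, with no change to data collection, sample size or any test.
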